**Coronary ARteriogenesis with combined Heparin and
EXercise therapy in chronic refractory Angina (CARHEXA):
A phase 3 double-blind, placebo-controlled, parallel group
study**

December 25, 2012

ABSTRACT

Background: Although experimental studies on the stimulation of coronary arteriogenesis have been promising, not a single drug has been proved to be applicable in clinical practice, either due to lack of efficacy or because of undesired side effects. Encouraging results have been obtained with combination of heparin (H) coupled with a stress inducing ischemia and augmenting shear stress, such as exercise.

Aim: to establish the coronary arteriogenetic efficacy of H combined with exercise in patients with intractable coronary artery disease.

Methods: We will recruit 60 "no-option" patients with chronic stable angina refractory to optimal medical management, and not suitable for percutaneous and/or surgical revascularization therapy. As further inclusion criteria eligible patients are able to exercise (and enter a cardiac rehabilitation program). In a prospective, randomized, double-blind study design these "no-option" patients will be allocated (30 for each of the 2 groups) to one of 2 treatment groups: 1) standard physical rehabilitation (i.v. placebo 10 min prior to each of 2 exercise session per day for 5 days a week for 2 weeks); 2) drug-primed physical rehabilitation (same modality as 1, but with H, 100 UI/Kg up to a maximum of 5.000 IU iv, 10 min prior to the exercise). All patients will undergo exercise stress echo (with wall motion score index, coronary flow reserve on left anterior descending and global longitudinal strain evaluation) and cardiac CT (with coronary collateral assessment) both before and after the therapy cycle.

Endpoints. Clinical and imaging (by blinded observers) assessment will be performed before and after treatment. **Primary clinical endpoint** is Canadian Cardiovascular Society (CCS) angina severity, ranging from class 1 (mild) to 4 (severe). **Secondary stress imaging functional endpoint** is peak Wall Motion Score Index (WMSI) at stress echo (ancillary endpoints: global longitudinal strain and coronary flow reserve). **Tertiary imaging endpoint** is Coronary Collateral Circulation Score at cardiac CT.

Epidemiological and clinical background

The optimal treatment of coronary artery disease (CAD) involves reducing the ischemic burden, lowering the risk of future adverse cardiac events, and relieving symptoms of angina pectoris. Medical and mechanical therapies have played a major role in reducing the morbidity and mortality associated with ischemic heart disease. Despite the success of these conventional therapies, there are patients with coronary artery disease (CAD) who continue to experience angina despite maximal medical and revascularization therapy. Therapeutic angiogenesis represents a novel treatment option for these “no-option” patients with refractory ischemic coronary disease. A growing body of evidence has revealed the potential of therapeutic angiogenesis with gene, protein, or cell-based therapies. The goal of therapeutic angiogenesis is to induce the formation of new vessels that can enhance blood flow to areas that no longer have adequate blood supply. Although cardiovascular mortality attributable to ischemic heart disease has recently declined, it is still the leading cause of death in the Western countries. The associated morbidity and mortality of ischemic heart disease produces a considerable burden on the healthcare system. The number of patients with chronic stable angina has been estimated to be 16,500,000 (*Gibbons et al, 2003*). Given the ongoing obesity epidemic, increased incidence of diabetes mellitus, and an aging population, this impressive number will likely continue to grow. With a better understanding of the patho-physiology of ischemic heart disease over the last several decades, there have been tremendous advances in the treatment of CAD. Novel pharmacological agents, improved revascularization techniques, and better risk assessment tools have enabled healthcare practitioners to manage patients with ischemic heart disease more efficiently. Despite these advances, there is a growing population of patients who continue to be disabled by chronic angina. Healthcare providers have numerous treatment options to provide angina relief for these patients. Current guidelines for chronic stable angina recommend quitting smoking, blood pressure control, intensive lipid-lowering therapy, adequate physical activity, achievement of ideal body weight, and diabetes control. Medications routinely prescribed include anti-platelet therapy, statins, angiotensin-converting enzyme (ACE) inhibitors, beta-blockers, calcium channel blockers, nitrates and more recently ranolazine. Revascularization either with percutaneous coronary intervention or surgical bypass is part of the management of chronic CAD as well. When standard treatment measures are inadequate to control angina, novel approaches are needed. The European Society of Cardiology has defined refractory angina as a “chronic condition (>3 months) characterized by the presence of angina caused by coronary insufficiency in the presence of CAD which cannot be controlled by a combination of medical

therapy, angioplasty, and coronary bypass surgery” (*Mannheimer C et al, 2002*). Although the epidemiology of refractory angina is unclear and descriptive epidemiological studies are urgently needed, recent data indicate that the number of patients with refractory angina not amenable to revascularization on optimal medical therapy (“no-option” patients) is at least 150,000 per year in the US alone (*Williams B et al. 2010*).

The clinically elusive goal of therapeutic coronary arteriogenesis

Patients with severe CAD commonly develop collateral flow to ischemic myocardial territories that ameliorate or in some cases, eliminate myocardial ischemia. However, there are many patients in whom this patho-physiological angiogenic response is inadequate to control angina symptoms. After birth, new blood vessel formation proceeds via angiogenesis or arteriogenesis. Angiogenesis (capillary sprouting) results in higher capillary density. Arteriogenesis (rapid production of collateral arterioles) is potentially able to significantly alter the outcome of coronary and peripheral artery disease. The processes share some growth factors but differ in many respects. Arteriogenesis is by far the most efficient adaptive mechanism for the survival of the internal organs such as heart because of its ability to conduct, after adaptive growth, relatively large blood volumes per unit of time. An increase in the number of capillaries, the results of stimulated angiogenesis, is unable to do this (*Buschmann I and Schaper W, 1999*).

The goal of therapeutic angiogenesis is to enhance the formation of new vessels that can provide arterial blood flow to myocardial regions with inadequate blood supply. Therapeutic angiogenesis can be accomplished using three approaches: gene therapy delivered locally (FGF and VEGF); cytokines stimulating angiogenesis (MP1, PIGF, etc); hematopoietic/angiogenic stem cells. Although experimental studies on the stimulation of arteriogenesis has been promising, not a single drug have been proved to be applicable in clinical practice, either due to lack of efficacy or because of undesired side effects (*Schirmer et al 2009*).

Pharmacologic approaches to enhance coronary arteriogenesis.

Our approach is based on the combination of pharmacological stimuli (with heparin) on top of a 2-week cycle of physical rehabilitation (in patients capable to exercise). The rationale for this chemical-physical cocktail stems from the fact that increase in shear stress (achieved with exercise), or heparin – when used alone - have no significant coronary arteriogenic effect, which is consistently present, and clinically significant, when the two stimuli are coupled (*Fujita M et al. 1988*). The basic principle of heparin treatment is potentiation of angiogenic growth factors, which

are overexpressed by increased shear stress at the site of pre-existing collateral vessels as a result of exercise or pacing. Although the precise mechanisms by which heparin potentiates arteriogenesis remain to be completely elucidated, heparin administration combined with exercise (*Tateno S et al 2001*) has great potential in treating patients with effort angina who are not indicated for conventional reperfusion therapy.

Study hypothesis

In the large and expanding population of "no-option" patients with refractory angina, a clinically significant coronary arteriogenic effect can be obtained through a combination of pharmacological (heparin) and physical (rehabilitation exercise program) stimuli, when used in combination.

Overall study design

We will recruit 60 patients with chronic stable angina refractory to medical management, and not suitable for percutaneous and/or surgical revascularization therapy. As additional criterion for treatment eligibility, patients will have exercise capacity allowing to enter a rehabilitation program. In a prospective, randomized, open-label study design these "no-option" patients will be allocated (30 for each group) to 2 treatments: 1) standard physical rehabilitation (2 exercise session per day for 5 days a week for 2 weeks); 2) drug-primed physical rehabilitation (same modality as 1, but with H, 100 UI/Kg up to a maximum of 5.000 IU iv, 10 min prior to the exercise). All patients will undergo exercise stress echo (with wall motion score index, coronary flow reserve on left anterior descending and global longitudinal strain evaluation) and cardiac CT (with coronary collateral assessment) both before and after then therapy cycle.

Inclusion criteria: patients with documented coronary artery disease not amenable of further treatment and belonging to the "no-option" category (see above definition), with symptoms consistent with angina pectoris.

Exclusion criteria: patients with unstable angina, recent acute myocardial infarction, uncontrolled hypertension, haemodynamically significant valvular heart disease, bronchial asthma and neurologic and/or orthopedic illnesses that limit exercise capacity will be excluded. Patients receiving vitamin K antagonist will be excluded. Patients should not be actively involved in programmes of cardiac rehabilitation or exercise training.

All medications will remain unaltered during the study

Clinical and imaging (by blinded observers) assessment will be performed before and after treatment. **Primary clinical endpoint** is Canadian Cardiovascular Society (CCS) angina severity, ranging from class 1 (mild) to 4 (severe). **Secondary stress imaging functional endpoint** is peak Wall Motion Score Index (WMSI) at stress echo (ancillary endpoints: global longitudinal strain and coronary flow reserve). **Tertiary imaging endpoint** is Coronary Collateral Circulation Score at cardiac CT.

Detailed Work Plan

The overall architecture of the project is structured into work-packages (WP) that will be run by separate teams, in parallel with each other:

WP0- Study design and statistical plan

WP1- Patient recruitment and treatment

WP2-Assessment of treatment effect on inducible ischemia by stress echo

WP3- Assessment of Coronary Collateral Circulation by MDCT

WP0- Study design and Statistical plan

Sample size calculation. The study is sized to detect with 80% power a clinically significant difference in the chosen endpoints with $\alpha=0.05$. For primary endpoint, a Canadian Class Angina = 2.5, with 0.5 standard deviation, and with an expected, clinically significant improvement of 0.5 will lead to a sample size of 16 patients per arm (94 % power with 25 patients per arm). For secondary endpoint, a peak WMSI = 1.4, with 0.25 standard deviation, and with an expected, clinically significant improvement of 0.2 will lead to a sample size of 25 patients per arm. Overall a drop-out rate of 20 % is expected, and therefore 60 patients will be initially considered and 50 are expected to complete the trial (25 for each arm)

Statistical plan: All continuous data will be given as mean+ SD. Baseline characteristics between the groups will be analyzed by Student t test for continuous data and chi-square/Fisher exact test for categorical data. Outcomes at follow-up examinations will be analyzed with chi-square test (for angina class) and paired Student t test (for approximately normally distributed data such as Wall Motion score index). Differences are considered statistically significant at a 2-sided P value of

<0.05. Electronic Case Report form preparation, ad interim and final data analysis will be performed by the Biometry Unit of the Institute of Clinical Physiology.

Core lab reading: All imaging data will be read by a single reader blinded to patient identity and study conditions.

Expected results: The group treated with active drug therapy will show a significant improvement of clinical, functional and perfusion indices when compared to standard rehabilitation therapy

WP1- Patient recruitment and treatment

CARHEXA is a prospective, randomized, single-center study: clinical enrollment and data collection will be done by Belgrade Unit. The Belgrade center has a recent tradition of clinical and scientific excellence in the field of diagnosis and treatment of coronary artery disease and has the facilities required to complete the study.

Ethical Committee submission will be presented at local authority by the Belgrade Unit, also responsible of clinical enrollment and data collection. We will recruit 60 patients with chronic stable angina refractory to medical management and not suitable for percutaneous and/or surgical revascularization therapy (see the above definition of “no-option” patients). In a prospective, randomized, open-label study design these "no-option" patients will be allocated (30 for each of the 2 groups) to one of 2 treatment groups: 1) standard physical rehabilitation (2 exercise session per day for 5 days a week for 2 weeks) with placebo (iv saline 10 min prior to exercise) ; 2) drug-primed physical rehabilitation (same modality as 1, but with H, 100 UI/Kg up to a maximum of 5.000 IU iv, 10 min prior to the exercise).

The Canadian Cardiovascular Society (CCS) classification of angina severity, ranging from class 1 (mild) to class 4 (severe), is used routinely in patients with coronary artery disease and is a recognized marker for disease progression.

The SAQ is a 19- item questionnaire that measures 5 clinically important dimensions of health in patients with CAD: angina frequency, angina stability, physical limitations, treatment satisfaction, and disease perception/QOL. Each domain has a score ranging from 0 to 100, with higher scores indicating less disease burden. The quality of life assessed with SAQ has been shown to correlate with long-term survival and hospitalization for acute coronary syndrome among patients with chronic CAD (*Spertus JA et al, Circulation 2002*).

Intravenous injections will be given by a study nurse not involved in the process of data acquisition and analysis.

WP2: Assessment of treatment effect on inducible ischemia by Stress Echo

Background: Stress echocardiography is an established technique for the diagnostic and prognostic evaluation of coronary artery disease. Wall motion score index assesses in a semi-quantitative way the extent of inducible ischemia, which is related to the anatomic and prognostic severity of underlying coronary artery disease. Noninvasive external pacing has the same accuracy as other physical and pharmacological stressors, and can be the first-choice option in patients with permanent pacemaker (Sicari *et al.* 2009).

Methods: All patients will undergo a resting echo and a stress echo, with either heparinized exercise (Group 1) or exercise (Group 2), according to standard clinical protocol (Sicari *R et al, Eur Heart J* 2009). Resting echo will assess all left ventricular function and remodeling indices, as previously described (Bolognese L *et al, Circulation* 2004). No change in underlying optimal conventional medical therapy will be done, except for clinically driven reasons, during the study period. Wall Motion Score Index (each segment from 1=normal to 4=dyskinetic in a 17 segment model of left ventricle) will be calculated at baseline and peak stress following the standard protocols of European Association of Echocardiography. In all patients a quantitative assessment of longitudinal strain by 2D speckle tracking will be performed.

WP3: Assessment of Coronary Collateral Circulation by MDCT

Cardiac CT will be performed to assess coronary collateral circulation in all patients before and after 2-week exercise. A collateral circulation will be graded by coronary CT *angiography* score where 0-2 means poorly developed collaterals and score 3 will be considered as well developed collaterals (0 = absence of distal filling; 1 = partial distal filling, with a length less than one-third of the segment; 2 = partial distal filling, with a length between one-third and two-thirds of the segment; 3 = complete or partial distal filling, with a length longer than two-thirds of the segment). CT angiography scores correspond fully to Rentrop classificatio. Also we will look for change in growth of baseline bridging collaterals at 2 weeks (0 = not present, 1 = present).

References

- Barron HV**, et al. Effects of the repeated administration of adenosine and heparin on myocardial perfusion in patients with chronic stable angina pectoris. *Am J Cardiol* 2000; 85: 1-7
- Bolognese L**, et al. Impact of microvascular dysfunction on left ventricular remodeling and long-term clinical outcome after primary coronary angioplasty for acute myocardial infarction. *Circulation*. 2004;109:1121-6.
- Bombardini T**, Picano E: The coronary angiogenetic effect of heparin: experimental basis and clinical evidence. *Angiology* 1997; 48: 969-76
- Buschmann I**, Schaper W. Arteriogenesis Versus Angiogenesis: Two Mechanisms of Vessel Growth. *News Physiol Sci*. 1999;14:121-125
- Fujita M**, et al. Improvement of treadmill capacity and collateral circulation as a result of exercise with heparin pretreatment in patients with effort angina. *Circulation*. 1988;77:1022-9
- Gibbons RJ**, et al. ACC/AHA 2002 guideline update for the management of patients with chronic stable angina: a report of the American College of Cardiology/American Heart Association Task Force on Practice Guidelines (Committee to Update the 1999 Guidelines for the management of Patients with Chronic Stable Angina. *Circulation* 2003; 107: 149 – 158
- Mannheimer C**, et al. The problem of chronic refractory angina; report from the ESC Joint Study Group on the Treatment of Refractory Angina. *Eur Heart J*. 2002;23:355-70
- Meier P**, et al. Myocardial salvage through coronary collateral growth by granulocyte colony-stimulating factors in chronic coronary disease: a controlled randomized trial. *Circulation* 2009; 120 ; 1355-1363

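### The only anticoagulant exclusion names vitamin K antagonists, so patients on another anticoagulant, or with a known reason not to receive heparin, can be randomised to 20 heparin injections

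*Combined protocol and SAP*

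**What the plan says.** The exclusion criteria under Overall study design are the only exclusion list in the document. They bar "patients with unstable angina, recent acute myocardial infarction, uncontrolled hypertension, haemodynamically significant valvular heart disease, bronchial asthma", and go on to "neurologic and/or orthopedic illnesses that limit exercise capacity will be excluded". Two items follow: "Patients receiving vitamin K antagonist will be excluded", and a bar on patients already active in a rehabilitation or training programme.

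Two sentences govern background treatment. Directly after the exclusion list: "All medications will remain unaltered during the study". In the Methods of WP2 (Stress Echo): "No change in underlying optimal conventional medical therapy will be done, except for clinically driven reasons, during the study period".

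The experimental arm receives heparin at "100 UI/Kg up to a maximum of 5.000 IU iv, 10 min prior to the exercise" (Abstract, Overall study design and WP1). The training schedule is "2 exercise session per day for 5 days a week for 2 weeks". In the Abstract, the control arm receives "i.v. placebo 10 min prior to each of 2 exercise session per day for 5 days a week for 2 weeks", and the heparin arm follows the same schedule.

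**The concern.** A trial whose only investigational drug is an anticoagulant bars one class of anticoagulant and is silent on every other. It is also silent on whether a patient is suitable for heparin at all. The medication rule then keeps whatever the patient takes at entry.

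Two different things are at stake:

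- **Safety in the heparin arm.** A patient on another anticoagulant, or with a known reason not to be given heparin, passes the written criteria and can be allocated to repeated heparin. The document describes no bleeding or platelet monitoring, so eligibility is where a written safeguard would be expected.
- **Contrast between arms, for background heparin only.** The study rationale says that neither heparin nor exercise has a significant effect alone and that the two together do. A control patient on background heparin who trains may get part of that combination.

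**Working it through.** **1. What the exclusion list covers.**

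| Exclusion | Stated in terms of anticoagulation, bleeding or heparin? |
|---|---|
| Unstable angina | No |
| Recent acute myocardial infarction | No |
| Uncontrolled hypertension | No |
| Significant valve disease | No |
| Bronchial asthma | No |
| Neurologic or orthopedic limits to exercise | No |
| Vitamin K antagonist use | Yes, one class |
| Current rehabilitation or training | No |

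The rest of the document adds no rule on other oral anticoagulants, on background heparin of any kind, or on suitability for heparin.

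**2. Following one patient through the rules.** Take a no-option patient on an anticoagulant that is not a vitamin K antagonist.

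- Exclusion list: no item applies, so the patient is eligible.
- Medication rule in Overall study design: the drug continues.
- Medication rule in WP2: the drug may be changed for a clinical reason. This operates during the study and case by case. It does not stop randomisation.
- Allocation: 30 per arm, so the chance of the heparin arm is one half.

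A patient with a known reason not to receive heparin follows the same path.

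**3. Exposure.** Sessions per day x days per week x weeks = 2 x 5 x 2 = 20 training sessions, with one injection before each. A heparin-arm patient who completes the programme receives 20 heparin injections.

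**4. How far contamination follows.** The section on pharmacologic approaches credits the effect to heparin, through potentiation of angiogenic growth factors, coupled with exercise. Background heparin in a control patient is therefore relevant. Nothing in the document says that other anticoagulants act in this way. A reason not to receive heparin has no bearing on a saline arm.

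**5. What dilution could do (illustration only).** The plan's own figures come first, by the normal approximation with two-sided alpha 0.05 and 1:1 allocation:

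- n per arm = 2 x (1.96 + 0.84)² x (SD/difference)².
- CCS class (SD 0.5, difference 0.5): 15.7, so 16 per arm, as stated. Power with 25 per arm is 94.2%, against a stated 94%.
- Peak WMSI (SD 0.25, difference 0.2): 24.5, so 25 per arm, as stated. Power with 25 per arm is 80.7%.

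Now assume that a fraction f of control patients takes background heparin and obtains the full effect. The difference becomes (1 − f) times the planned one, and power = Φ[difference / (SD x √(2/25)) − 1.96].

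| f (assumed) | CCS difference | CCS power | WMSI difference | WMSI power |
|---|---|---|---|---|
| 0% | 0.500 | 94.2% | 0.200 | 80.7% |
| 5% | 0.475 | 91.9% | 0.190 | 76.6% |
| 10% | 0.450 | 88.9% | 0.180 | 72.1% |
| 20% | 0.400 | 80.7% | 0.160 | 61.9% |
| 30% | 0.350 | 69.7% | 0.140 | 50.8% |

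No value of f is given or implied by the document, and the full-effect assumption is the worst case for each f. The table shows the direction and the sensitivity. It does not estimate the loss.

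**The case against.** The strongest case on the other side has five parts.

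- **A reader might infer that any overlooked anticoagulant contaminates the placebo arm.** The document does not support this. Its mechanism is specific to heparin with exercise; for other classes the concern is safety in the heparin arm.
- **A reader might infer that a placebo patient on background heparin simply receives the experimental treatment.** That also goes too far. The study regimen is a weight-based intravenous dose shortly before each session, and the document does not show that heparin by another dose, route or timing is equivalent. Excluding unstable angina and recent infarction probably removes some heparin users as well. What stands is that partial contamination is possible.
- **A reader might infer that the plan makes the overlap unavoidable.** The WP2 exception for clinically driven changes shows that it does not. That exception still leaves eligibility untouched.
- **The protocol gives no reason for barring vitamin K antagonists.** Avoiding overlapping anticoagulation is a plausible motive but an inferred one. The gap does not depend on it: the criterion admits these patients whatever its purpose.
- **Investigators would probably screen such patients out by ordinary judgement.** Perhaps so, but that practice would be unwritten, unrecorded and liable to vary from patient to patient.

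On power, even the worst-case illustration leaves the primary endpoint above the 80% target up to f = 20%. The validity half alone would be a modest point.

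**Conclusion.** The concern holds as a safety gap in eligibility. The written criterion itself admits patients on non-vitamin-K anticoagulants or background heparin, and patients with a known reason not to receive heparin. Such a patient can be allocated to 20 heparin injections. This rests on the exclusion list being complete as written; no other section closes the gap.

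The number of patients affected is unknown. The document gives no frequency of use, and any percentage would be an unanchored assumption.

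The dilution of the treatment contrast is a secondary and conditional point. It applies only to background heparin in the control arm, it may be partial, and its size cannot be estimated from the document. No sample size or power figure in the plan is wrong because of it.

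The change should be made: it is cheap and it protects patients. The gap does not by itself invalidate the design.

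**What to change.** The sponsor should reconcile three things: the exclusion limited to vitamin K antagonists, the two differing statements on background medication (Overall study design and WP2), and the heparin regimen in WP1. The single-class criterion should be replaced by one that covers concurrent anticoagulation in general, including background heparin, and suitability for heparin. Which drugs and which conditions belong on the list is the sponsor's clinical decision and is not proposed here. The criterion should be checked and recorded at screening, before randomisation, so that it applies equally to both arms.

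Cost: a revised exclusion criterion, aligned medication wording, a check of history and current drugs at screening, and a few more screen failures. If the sponsor's list relies on a laboratory value, that may add a test, since the document mentions no screening blood count.

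### The 94% power for the primary endpoint rests on an unsourced SD that is the smallest a CCS class can have at mean 2.5, so it is a best case, and it describes a test other than the planned one

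*Combined protocol and SAP*

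**What the plan says.** The sample-size calculation under WP0 states its aim: "The study is sized to detect with 80% power a clinically significant difference in the chosen endpoints", at alpha 0.05. For the primary endpoint the planning values are "a Canadian Class Angina = 2.5, with 0.5 standard deviation" and, for the effect, "with an expected, clinically significant improvement of 0.5 will lead to a sample size of 16 patients per arm". The same sentence adds "94 % power with 25 patients per arm". The 25 per arm is the number derived for the secondary endpoint, peak WMSI, and is also the expected number of completers in each arm out of 60 enrolled.

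The primary endpoint is CCS angina class, "ranging from class 1 (mild) to 4 (severe"). The inclusion criteria require documented, no-option coronary disease "with symptoms consistent with angina pectoris". Neither the inclusion nor the exclusion criteria set a limit on CCS class.

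The paragraph gives no source for the SD. It does not say whether 0.5 is the SD at baseline, at follow-up or of the change; the wording attaches it to the class value of 2.5. The Statistical plan tests angina class at follow-up with a chi-square test, two-sided at 0.05, and names no adjustment for baseline class.

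**The concern.** A planning SD should be a plausible value for the patients to be enrolled. Here it coincides with a mathematical floor: at the planned mean, no whole-number score can vary less. Any patient in class 1 or class 4 pushes the SD of a group with mean 2.5 above 0.5, and power under the stated model falls quickly as that happens.

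The figure matters because this is the only sizing given for the primary endpoint, and 94% suggests a comfortable reserve over the 80% target. If the primary result were null, a reader would take it as coming from a trial that had a 94% chance of finding a half-class effect. The figure also comes from a comparison of means, while the plan compares class frequencies.

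**Working it through.** **Inputs.** From the sample-size paragraph: mean class 2.5, SD 0.5, difference 0.5, alpha 0.05, 80% power, 25 completers per arm. From the Statistical plan: two-sided testing, chi-square for angina class. From the endpoint definition: classes 1 to 4. Every other SD and class distribution below is an assumption.

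**1. Reproducing the stated figures** (two means, common SD, normal approximation)

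- n per arm = 2 × (1.960 + 0.842)² × (SD/difference)² = 2 × 7.85 × (0.5/0.5)² = 15.7, so 16.
- Power at 25 per arm = Φ(0.5 / (0.5 × √(2/25)) − 1.960) = Φ(3.536 − 1.960) = Φ(1.576) = 94.2%.

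Both agree with the plan. The exact t-test gives 17 per arm and 93.4%, which is only a difference of formula.

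**2. The floor.** Every whole-number class lies at least 0.5 away from 2.5. The mean squared deviation from 2.5 is therefore at least 0.25, and the SD at least 0.5. Equality holds only if everyone is in class 2 or 3, which at mean 2.5 means half in each.

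**3. Leaving the floor.** If a share q of patients is split evenly between classes 1 and 4 and the rest evenly between 2 and 3, the variance is 0.25(1 − q) + 2.25q = 0.25 + 2q. Using that SD in both arms, as the plan's model does, the t-test power for a difference of 0.5 with 25 per arm is:

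| q (assumed) | SD = √(0.25 + 2q) | Power |
|---|---|---|
| 0% | 0.50 | 93% |
| 5% | 0.59 | 83% |
| 10% | 0.67 | 73% |
| 20% | 0.81 | 58% |
| 30% | 0.92 | 47% |

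At round SDs, power is 82% at 0.6, 58% at 0.8 and 49% at 0.9. It reaches 80% at an SD of about 0.62, that is q = (0.618² − 0.25)/2 = 0.066, or about 7% of patients in class 1 or 4.

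**4. Where the floor does not bind.** Under the planned effect the treated mean is 2.0, where the minimum SD is 0. Take a control arm of 5/45/45/5% in classes 1 to 4 (variance 0.45, SD 0.67):

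- If every class 3 and 4 patient drops one class, the treated arm is 5/90/5/0%, with variance 0.10 and SD 0.32. The pooled SD is √((0.45 + 0.10)/2) = 0.52 and power is about 91%.
- If the improvement is spread evenly over classes 2 to 4, each such patient drops one class with probability 0.5/0.95 = 0.526. The treated variance is 0.62 and the SD 0.79. The pooled SD is √((0.45 + 0.62)/2) = 0.73 and power is about 66%.

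The same control distribution is thus compatible with 91% or 66%.

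**5. If 0.5 was meant as a change or adjusted SD.** With an assumed raw SD of 0.8 and before-after correlation r, the baseline-adjusted SD is 0.8 × √(1 − r²). For r = 0.6 this is 0.64 (power about 77%); for r = 0.8 it is 0.48 (about 95%). The change-score SD, 0.8 × √(2(1 − r)), is 0.72 (about 68%) and 0.51 (about 93%) respectively.

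**6. The planned test.** In a simulation with 25 per arm, control 0/50/50/0% and treated 12.5/75/12.5/0% (SD 0.5 in both arms, difference 0.5), the chi-square test had about 86% power against 94% for the t-test. This is one illustrative case.

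**The case against.** The arithmetic is correct for its inputs, so this is not a calculation error. The declared target is 80%; the 94% is a parenthesis. With 25 per arm, the 80% target survives any common SD up to about 0.62. The 25 per arm comes from the WMSI calculation, so the CCS SD did not set enrolment. All of this stands.

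The entry criteria, although silent on CCS class, may narrow the spread. Patients must have refractory angina yet be fit for two exercise sessions a day, and unstable angina is excluded. That plausibly thins both ends of the scale. It does not empty them, and the plan does not make the argument.

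The floor applies only at mean 2.5, not to the treated arm at 2.0 and not to a change score. This also stands, and it means that patients in class 1 or 4 do not by themselves fix the loss. It does not rescue the stated figure: the plan's formula uses one common SD attached to the class value of 2.5, and the Statistical plan contains no change-score or baseline-adjusted analysis of CCS that a smaller SD could refer to.

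A reader might go further and infer that the trial fails to deliver 94% power, or is underpowered. The documents do not support that. They give no CCS distribution, so every figure below 94% under the means model depends on an assumed SD.

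**Conclusion.** The concern holds in a limited form. The stated 16 per arm and 94% are reproducible, but the SD behind them is unsourced and equals the minimum possible for a whole-number class with mean 2.5. Under the plan's common-SD model, 94% is a best case. Over assumed SDs of 0.6 to 0.9 the corresponding t-test power is 82% to 49%. How far actual power falls depends on three things the documents leave open: the class distribution of the enrolled patients, which patients improve, and which SD was meant. Separately, and whatever the SD, the 94% belongs to a comparison of means and should not be quoted as the power of the chi-square test. It is neither an arithmetic mistake nor evidence that 60 patients are too few.

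**What to change.** Keep enrolment at 60.

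1. State which SD 0.5 is (class at one time point, change, or residual after baseline adjustment) and what it is based on.
2. Replace the single 94% with power at the planned number of completers over a stated SD range, for example 0.5 to 0.9. Label the range as assumed, and identify 0.5 as the lower bound for a class score with mean 2.5. The completer number should be consistent too: 20% drop-out from 60 leaves 48, not 50, which moves the power by only about one point.
3. Compute that power for the test that will be used.
4. Analyse follow-up CCS class with a method that uses its ordering and adjusts for baseline class, for example a proportional-odds model with baseline class as covariate, so that the power statement and the analysis match. Baseline class is already collected, since clinical assessment is planned before and after treatment.

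The cost is a less favourable stated power, rewording of two paragraphs and slightly more analysis work. No patients, visits or measurements are added.
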